#### 7.2.3.3 Protocol-Specific Exceptions to Serious Adverse Event Reporting

Efficacy endpoints as outlined in this section will not be reported to the Sponsor as described in Section 7.2.3 - Immediate Reporting of Adverse Events to the Sponsor.

Specifically, the suspected/actual events covered in this exception include any event that is disease progression of the cancer under study.

The Sponsor will monitor unblinded aggregated efficacy endpoint events and safety data to ensure the safety of the subjects in the trial. Any suspected endpoint which upon review is not progression of the cancer under study will be forwarded to global safety as a SAE within 24 hours of determination that the event is not progression of the cancer under study.

#### 7.2.4 Evaluating Adverse Events

An investigator who is a qualified physician will evaluate all adverse events according to the NCI Common Terminology for Adverse Events (CTCAE), version 4.0. Any adverse event which changes CTCAE grade over the course of a given episode will have each change of grade recorded on the adverse event case report forms/worksheets.

All adverse events regardless of CTCAE grade must also be evaluated for seriousness.

Table 10 Evaluating Adverse Events

An investigator who is a qualified physician, will evaluate all adverse events as to:

V4.0 CTCAE Grading	Grade 1	Mild; asymptomatic or mild symptoms; clinical or diagnostic observations only; intervention not indicated.
	Grade 2	Moderate; minimal, local or noninvasive intervention indicated; limiting age-appropriate instrumental ADL.
	Grade 3	Severe or medically significant but not immediately life-threatening; hospitalization or prolongation or hospitalization indicated; disabling; limiting self-care ADL.
	Grade 4	Life threatening consequences; urgent intervention indicated.
	Grade 5	Death related to AE
Seriousness	A serious adverse event is any adverse event occurring at any dose or during any use of Sponsor's product that:	
	†Results in death; or	
	†Is life threatening; or places the subject, in the view of the investigator, at immediate risk of death from the event as it occurred (Note: This does not include an adverse event that, had it occurred in a more severe form, might have caused death.); or	
	†Results in a persistent or significant disability/incapacity (substantial disruption of one's ability to conduct normal life functions); or	
	†Results in or prolongs an existing inpatient hospitalization (hospitalization is defined as an inpatient admission, regardless of length of stay, even if the hospitalization is a precautionary measure for continued observation. (Note: Hospitalization for an elective procedure to treat a pre-existing condition that has not worsened is not a serious adverse event. A pre-existing condition is a clinical condition that is diagnosed prior to the use of a Merck product and is documented in the patient's medical history.); or	
	†Is a congenital anomaly/birth defect (in offspring of subject taking the product regardless of time to diagnosis); or	
	Is a new cancer (that is not a condition of the study) (although not serious per ICH definition, is reportable to the Sponsor within 24 hours to meet certain local requirements); or	
	Is an overdose (whether accidental or intentional). Any adverse event associated with an overdose is considered a serious adverse event for collection purposes. An overdose that is not associated with an adverse event is considered a non-serious event of clinical interest and must be reported within 24 hours.	
	Other important medical events that may not result in death, not be life threatening, or not require hospitalization may be considered a serious adverse event when, based upon appropriate medical judgment, the event may jeopardize the subject and may require medical or surgical intervention to prevent one of the outcomes listed previously (designated above by a †).	
Duration	Record the start and stop dates of the adverse event. If less than 1 day, indicate the appropriate length of time and units	
Action taken	Did the adverse event cause the Sponsor's product to be discontinued?	
Relationship to Sponsor's Product	Did the Sponsor's product cause the adverse event? The determination of the likelihood that the Sponsor's product caused the adverse event will be provided by an investigator who is a qualified physician. The investigator's signed/dated initials on the source document or worksheet that supports the causality noted on the AE form, ensures that a medically qualified assessment of causality was done. This initialed document must be retained for the required regulatory time frame. The criteria below are intended as reference guidelines to assist the investigator in assessing the likelihood of a relationship between the test drug and the adverse event based upon the available information.  The following components are to be used to assess the relationship between the Sponsor's product and the AE; the greater the correlation with the components and their respective elements (in number and/or intensity), the more likely the Sponsor's product caused the adverse event (AE):	
Relationship to Sponsor's Product	Exposure	Is there evidence that the subject was actually exposed to the Sponsor's product such as: reliable history, acceptable compliance assessment (pill count, diary, etc.), expected pharmacologic effect, or measurement of drug/metabolite in bodily specimen?
	Time Course	Did the AE follow in a reasonable temporal sequence from administration of the Sponsor's product? Is the time of onset of the AE compatible with a drug-induced effect (applies to trials with investigational medicinal product)?
	Likely Cause	Is the AE not reasonably explained by another etiology such as underlying disease, other drug(s)/vaccine(s), or other host or environmental factors

Relationship to Sponsor's Product (continued)	The following components are to be used to assess the relationship between the test drug and the AE: (continued)	
	Dechallenge	Was the Sponsor's product discontinued or dose/exposure/frequency reduced? If yes, did the AE resolve or improve? If yes, this is a positive dechallenge. If no, this is a negative dechallenge. (Note: This criterion is not applicable if: (1) the AE resulted in death or permanent disability; (2) the AE resolved/improved despite continuation of the Sponsor's product; or (3) the trial is a single-dose drug trial); or (4) Sponsor's product(s) is/are only used one time.)
	Rechallenge	Was the subject re-exposed to the Sponsor's product in this study? If yes, did the AE recur or worsen? If yes, this is a positive rechallenge. If no, this is a negative rechallenge. (Note: This criterion is not applicable if: (1) the initial AE resulted in death or permanent disability, or (2) the trial is a single-dose drug trial); or (3) Sponsor's product(s) is/are used only one time). NOTE: IF A RECHALLENGE IS PLANNED FOR AN ADVERSE EVENT WHICH WAS SERIOUS AND WHICH MAY HAVE BEEN CAUSED BY THE SPONSOR'S PRODUCT, OR IF REEXPOSURE TO THE SPONSOR'S PRODUCT POSES ADDITIONAL POTENTIAL SIGNIFICANT RISK TO THE SUBJECT, THEN THE RECHALLENGE MUST BE APPROVED IN ADVANCE BY THE SPONSOR CLINICAL DIRECTOR AS PER DOSE MODIFICATION GUIDELINES IN THE PROTOCOL.
		The assessment of relationship will be reported on the case report forms /worksheets by an investigator who is a qualified physician according to his/her best clinical judgment, including consideration of the above elements.
Record one of the following		Use the following scale of criteria as guidance (not all criteria must be present to be indicative of a Sponsor's product relationship).
Yes, there is a reasonable possibility of Sponsor's product relationship.	There is evidence of exposure to the Sponsor's product. The temporal sequence of the AE onset relative to the administration of the Sponsor's product is reasonable. The AE is more likely explained by the Sponsor's product than by another cause.	
No, there is not a reasonable possibility of Sponsor's product relationship	Subject did not receive the Sponsor's product OR temporal sequence of the AE onset relative to administration of the Sponsor's product is not reasonable OR the AE is more likely explained by another cause than the Sponsor's product. (Also entered for a subject with overdose without an associated AE.)	

## 7.2.5 Sponsor Responsibility for Reporting Adverse Events

All Adverse Events will be reported to regulatory authorities, IRB/IECs and investigators in accordance with all applicable global laws and regulations, i.e., per ICH Topic E6 (R1) Guidelines for Good Clinical Practice.

## 8.0 STATISTICAL ANALYSIS PLAN

This section outlines the statistical analysis strategy and procedures for the study. If, after the study has begun, but prior to final database lock, changes made to primary and/or key secondary hypotheses, or the statistical methods related to those hypotheses, then the protocol will be amended (consistent with ICH Guideline E-9). Changes to exploratory or other non-confirmatory analyses made after the protocol has been finalized, but prior to final database lock, will be documented in a supplemental SAP (sSAP) and referenced in the Clinical Study Report (CSR) for the study. Post hoc exploratory analyses will be clearly identified in the CSR. Separate analysis plans (i.e., separate documents from the sSAP) will be developed to detail other planned analyses (i.e., those specific to the analysis of PK data, and future biomedical research

### 8.1 Statistical Analysis Plan Summary

Key elements of the statistical analysis plan are summarized below; the comprehensive plan is provided in subsequent sections.

Study Design Overview	A Phase IB Dose Exploration Trial with MK-8628, a Small Molecule Inhibitor of the Bromodomain and Extra-Terminal (BET) Proteins, in Subjects with Selected Hematologic Malignancies
Treatment Assignment	This is an open label study with dose-level-specific cohorts.
Analysis Populations	Efficacy: Treatment Full Analysis Set (FAS), which is the same as ASaT Safety: DLT evaluable, and All Subjects as Treated (ASaT)
Primary Endpoint(s)	Proportion of subjects experiencing at least one DLT in cycle 1 (day 1 to 21)
Secondary Endpoints	Proportion of subjects in different response categories per protocol specified response criteria for each tumor type (AML or DLBCL)
Statistical Methods for Key Efficacy/Immunogenicity/ Pharmacokinetic Analyses	Proportion of subjects in different response categories will be estimated using Exact method based on binomial distribution (Clopper-Pearson Interval) for each tumor type.
Statistical Methods for Key Safety Analyses	Count and percentage of DLT will be provided. The Bayes credible interval (80%) for DLT rate will be estimated based on a prior distribution of Beta (1,1).
Interim Analyses	During the dose escalation phase, regular assessment of DLT from the most recent cohort will be performed.
Multiplicity	This is an estimated study and no multiplicity adjustment will be implemented
Sample Size and Power	The study is designed to assess the safety of MK-8628 in subjects with selected hematologic malignancies. The small numbers per cohort are not intended for statistical hypotheses.  Up to 28 evaluable subjects (6-14 per two dose levels) will be included in each subject cohort (AML or DLBCL). This results in a study sample size of up to approximately 56 subjects. The final sample size will depend on the number of patients experiencing DLTs at each DL, and may be increased if additional DLTs are required.

## 8.2 Responsibility for Analyses/In-House Blinding

The statistical analysis of the data obtained from this study will be the responsibility of the Clinical Biostatistics department of the SPONSOR.

This trial is being conducted as an open-label study with dose level-specific cohorts.

## 8.3 Hypotheses/Estimation

Objectives of the study are stated in Section 3.0.

There are no statistical hypotheses for this study.

## 8.4 Analysis Endpoints

### 8.4.1 Safety Endpoints

The primary safety objective of this trial is to estimate proportion of subjects experiencing at least one DLT in cycle 1 (day 1 to 21) for each of the regimens and tumor type independently.

Other safety endpoints include incidence, severity and relationship of AEs, laboratory abnormalities, SAEs, discontinuations due to AEs, dose adaptations due to AEs

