**Hematologic Toxicity:**

AML

1. Pancytopenia with a hypocellular bone marrow and no marrow blasts lasting for  $\geq 6$  weeks after the start of a cycle. For subjects with AML who have a suspected DLT in case of pancytopenia with a hypocellular bone marrow and no marrow blast on Day 22 bone marrow aspiration, the DLT window will be extended to the first 2 cycles or Day 42 for repeat bone marrow confirmation. However, enrollment of additional patients at this dose level should not be delayed during the extended window for DLT in this situation assuming a confirmed DLT for such a subject would not affect a dose escalation or de-escalation decision.

DLBCL

1. Grade 4 hematologic toxicity lasting  $\geq 7$  days, except thrombocytopenia  
Grade 4 thrombocytopenia of any duration  
Grade 3 thrombocytopenia is a DLT if associated with bleeding
2. Febrile or infection related neutropenia, Grade 3 or Grade 4

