**Non-Hematologic Toxicity:**

1. Grade 4 non-hematologic toxicity (not laboratory)
2. Grade 3 non-hematologic toxicity (not laboratory) lasting  $> 3$  days despite optimal supportive care. Grade 3 nausea, vomiting or diarrhea will be considered a DLT if lasting more than 3 days despite optimal supportive care.
3. Any Grade 3 or Grade 4 non-hematologic laboratory abnormality, if
  - medical intervention is required, or
  - the abnormality leads to hospitalization, or
  - the abnormality persists for  $> 1$  week
4. Any of the following liver test abnormalities\*\* are observed (see also Section 12.8):
  - ALT or AST  $> 8X$  ULN
  - ALT or AST  $> 5X$  ULN for more than 2 weeks
  - ALT or AST  $> 3X$  ULN **AND** (total bilirubin  $> 2X$  ULN **OR** INR  $> 1.5$ )
  - ALT or AST  $> 3X$  ULN with the appearance of fatigue, nausea, vomiting, right upper quadrant pain or tenderness, fever, rash and/or eosinophilia ( $> 5\%$ ), unless the investigator assesses the rash or fatigue to be related to MK-8628 and not related to liver impairment with sponsor's agreement.

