**Other Toxicity:**

1. Any drug-related AE which caused subject to discontinue treatment during Cycle 1
2. Any study drug-related toxicity resulting in a subject missing  $\geq 20\%$  of planned doses during Cycle 1.
3. Any treatment-related toxicity which causes a greater than 2 week delay in initiation of Cycle 2.
4. Grade 5 toxicity

DLTs must be reported within 24 hours to the Sponsor as Events of Clinical Interest (see Section 7.2.3.2). If the event also meets the criteria for seriousness, follow the reporting guidelines for Serious Adverse Events (SAEs) outlined in Section 7.2.3.1.

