### **5.2.2 Timing of Dose Administration**

MK-8628 is to be administered orally with water in a fasted state, and as part of a BID regimen (twice daily, approximately 12 hours apart). Subjects should not have food for 1 hour before or 3 hours after study drug administration.

Dosing not performed at the same time ( $\pm 2h$ ) as on other days should be skipped. Subjects are to be instructed that if they vomit or omit their dose in that time frame, it is not to be replaced. Capsules must not be opened or chewed.

A treatment cycle is 21 days (3 weeks). The subsequent cycle will begin on day 22 or after recovery from any AEs to baseline or Grade < 2 associated with the previous cycle.

Subjects should receive study treatment within 3 days following treatment allocation.

Details of the exact dose and time of administration will be documented in a validated subject diary and reported in the electronic case report form (eCRF).

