## 8.5 Analysis Populations

### 8.5.1 Safety Analysis Populations

**DLT Evaluable population:** subjects who receive at least 85% of the planned dose of study drug (18 days) or experience DLT during the first 21-day cycle.

The **All Subjects as Treated (ASaT)** population, also known as **treated population**, consisting of subjects who receive at least one dose of study drug, will be used for the analysis of all other safety data in this study.

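### The SAP closes the primary DLT count at Day 21, but the protocol's AML marrow DLT window runs to Day 42 and its Cycle 2 delay DLT cannot be met until after Day 36

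*Combined protocol and SAP*

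**What the plan says.** The primary endpoint is stated twice in the SAP. The Section 8.1 summary gives "Proportion of subjects experiencing at least one DLT in cycle 1 (day 1 to 21"), and Section 8.4.1 says the aim is to "estimate proportion of subjects experiencing at least one DLT in cycle 1 (day 1 to 21"), by regimen and tumor type. Section 8.5.1 builds the DLT-evaluable population from subjects with at least 85% of the planned dose (18 days), "or experience DLT during the first 21-day cycle".

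Section 5.2.1.3 opens with the same 21-day cycle and then lists criteria that run past it:

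- **AML, hematologic.** The single AML-specific hematologic DLT is pancytopenia with a hypocellular, blast-free marrow lasting at least six weeks from the start of a cycle. It is suspected when there is hypocellularity and "no marrow blast on Day 22 bone marrow aspiration". In that case "the DLT window will be extended to the first 2 cycles or Day 42 for repeat bone marrow confirmation".
- **Both cohorts, other toxicity.** "Any treatment-related toxicity which causes a greater than 2 week delay in initiation of Cycle 2" is a DLT. Section 5.2.2 fixes the reference point: "The subsequent cycle will begin on day 22", or after recovery from adverse events.
- **Duration criteria.** Several need a minimum duration, for example ALT or AST above five times "ULN for more than 2 weeks".

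The 21-day wording also appears in Section 2.1, in the footnote to Table 3 and in the opening of Section 5.2.1.3. Section 8 mentions neither the AML extension nor any rule for a DLT that is confirmed after Day 21.

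**The concern.** The DLT rate is the endpoint that drives dose selection (Section 5.2.1.4), so its counting window should leave no choice to the analyst. As written, an analyst who follows Section 8 to the letter would classify an AML subject with a marrow DLT confirmed on Day 42 as DLT-free. An analyst who follows Section 5.2.1.3 would count the same subject as a DLT. The first analyst can only report a lower toxicity rate. With 6 to 14 subjects per dose level and cohort, a single event changes the estimate and its interval visibly.

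**Working it through.** **1. The plan's own figures.** The maximum sample size is 2 cohorts × 2 dose levels × 14 = 56, as stated. The 80% credible intervals in Table 11 are highest-density intervals of Beta(1+x, 1+n−x), which is the Beta(1,1) prior of Section 8.6.1 updated with x DLTs in n subjects. All 11 rows of that column reproduce to three decimals. For 0/6 the posterior is Beta(1,7) and the upper limit is 1 − 0.2^(1/7) = 0.205. For 1/6 it is Beta(2,6), giving (0.040, 0.391). Equal-tailed intervals do not match the table (0/6 would give 0.015 to 0.280).

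**2. When each criterion can be met.**

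- AML marrow DLT: six weeks is 42 days, and Section 5.2.1.3 names Day 42. That is 42 − 21 = 21 days after the SAP window closes. The aspirate that raises the suspicion, on Day 22, is itself nominally one day outside the window.
- Cycle 2 delay: Cycle 2 is due on Day 22, and 22 + 14 = 36. A delay of more than 14 days is first met on Day 37, which is 37 − 21 = 16 days after the window closes.
- Duration criteria, counting the onset day as day 1, with the latest onset that completes by Day 21: ALT/AST elevation for more than 2 weeks, Day 7; non-hematologic laboratory abnormality for more than 1 week, Day 14; DLBCL Grade 4 hematologic toxicity for 7 days or more, Day 15; Grade 3 non-hematologic toxicity for more than 3 days, Day 18. These can finish inside or outside the window, depending on onset.

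The first two can never be complete by Day 21.

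**3. Direction of the error.** Let x other subjects among n have a DLT, and let one further subject have only a late one. The correct rate is (x+1)/n.

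- If that subject received at least 85% of the dose, he or she stays in the denominator as a non-event: x/n < (x+1)/n.
- If not, Section 8.5.1 read literally removes the subject from both counts. Then x/(n−1) < (x+1)/n whenever x < n−1, with equality only if every other subject had a DLT.

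Among the same subjects, omission therefore never raises the rate.

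**4. Size of one uncounted event at n = 6.**

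| | Counted (1/6) | Not counted (0/6) |
|---|---|---|
| Observed rate | 16.7% | 0% |
| 80% interval (Table 11) | (0.040, 0.391) | (0, 0.205) |
| Posterior P(rate > 25%) | 44.5% | 13.3% |
| Table 4 entry | S | E |

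Other single-event steps in Table 4 also change the entry: 3/6 to 2/6 (D to S), 4/6 to 3/6 (DU to D), 3/14 to 2/14 (S to E) and 6/14 to 5/14 (D to S). Some do not: 2/6 to 1/6 stays S, and so does 4/14 to 3/14.

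**The case against.** The strongest reply is that Section 8 does not redefine a DLT. It repeats a window that Section 5.2.1.3 itself uses, and that section speaks of toxicities occurring during Cycle 1, not of criteria completed in Cycle 1. On that reading, a toxicity that arises in Cycle 1 and then delays Cycle 2, or lasts beyond Day 21, is a Cycle 1 DLT whose severity becomes known later. This largely stands for the delay and duration criteria. A reader might infer that the SAP excludes every late-finishing DLT. The documents do not support that, because Section 8 states no completion test. What remains for these criteria is that Section 8 does not state the rule.

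The reply does not dispose of the AML criterion. There the protocol says the window itself is extended, and the finding that starts the process is sought on Day 22. Section 5.2.1.3 says how enrollment proceeds while confirmation is pending, but not how the endpoint is counted.

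A reader might also infer that the gap moves the dose choice across the 25% level, since 4/14 is 28.6% and 3/14 is 21.4%. Both are S in Table 4, Section 5.2.1.2 accepts an observed rate slightly above or below 25% at the RP2D, and Section 5.2.1.4 makes RP2D selection multi-faceted. Nor do the documents show that any escalation decision went wrong.

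Two further points stand. Only subjects with no earlier DLT matter, and many toxicities severe enough to delay Cycle 2 may already qualify, for example Grade 4 thrombocytopenia in DLBCL or missing at least 20% of Cycle 1 doses. And the documents give no frequency for late DLTs. The nearest figure, Cycle 1 DLTs in 3 of 75 acute leukemia subjects (4%) in the preceding study (Section 4.1.1.3), comes from other doses and schedules and does not isolate late events.

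**Conclusion.** The inconsistency is real. For the AML marrow DLT, Sections 8.1, 8.4.1 and 8.5.1 directly contradict Section 5.2.1.3. For the Cycle 2 delay and the duration criteria it is an unstated counting rule, which the occurrence-in-Cycle-1 reading can resolve. Any resulting bias in the reported DLT rate is downward. The n = 6 example shows what one event would do; it is not an estimate of what happened, and no expected bias can be calculated from these documents. Enrollment is closed and the program has been terminated (Section 1.0), so the effect is mainly on the reported DLT rate. The correction is still worth making, because it concerns the primary endpoint and Section 10.7 intends publication even after early termination.

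**What to change.** In Sections 8.1, 8.4.1 and 8.5.1, replace the Day 1 to 21 limit with wording such as: *a DLT as defined in Section 5.2.1.3, including the extended AML window and the Cycle 2 delay criterion, for toxicity in Cycle 1 confirmed or completed after Day 21*. State that these subjects count in both numerator and denominator. Reconcile Section 2.1, the Table 3 footnote and the opening of Section 5.2.1.3 with the criteria that follow, without altering any DLT criterion. The text should stay this narrow: a rule that counted anything attributable to Cycle 1 dosing could take in toxicities first appearing in Cycle 2 and so widen the definition.

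The cost is wording only. A subject's DLT status may become final up to about three weeks later (Day 42 instead of Day 21). If the database is already locked, the clinical study report should state which counting rule was used.
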